5.4.8 Papanicolaou Test

DELETED:

~~This is not required for subjects who have had a full hysterectomy.~~

5 Treatments and Evaluation

5.8.7 Adverse Events of Special Interest

WAS:

Adverse events of special interest in this study will include:

- AE of uterine bleeding
- Endometrial hyperplasia/cancer or disordered proliferative endometrium
- AE of thrombocytopenia or platelets < 150000/uL
- AE of liver test elevations or elevation in ALT and/or AST > 3 × ULN
- AE of bone fractures/bone loss ≥ 7%

IS AMENDED TO:
Adverse events of special interest in this study will include: 
● AE of uterine bleeding● Endometrial hyperplasia/cancer or disordered proliferative endometrium● AE of thrombocytopenia or platelets < 150000/uL● AE of liver test elevations or elevation in ALT and/or AST > 3 × ULN● AE of bone fractures/bone loss ≥ 7%● AEs of abuse liability● AEs of depression● AEs of wakefulness● AEs of effect on memory

IV. Synopsis, Subject Discontinuation and 6 Discontinuation 6.1 Discontinuation of Individual Subject(s) From Study Treatment
ADDED:

● Category 2 results of secondary or tertiary screening endometrial biopsy diagnosis.

8 Operational Considerations 8.1.1 Electronic Clinical Outcome Assessment/Electronic Patient-reported Outcome
ADDED:
The daily diary compliance threshold for each individual subject should not fall below 85%. In cases where a subject's compliance falls below this threshold, the site should immediately retrain the subject and document this training in the subject's source.

7 Statistical Methodology 7.4.2.2 Secondary Endpoints
ADDED:
PGI-C will be analyzed using Cochran Mantel Haenszel test.

7 Statistical Methodology 7.4.3 Analysis of Exploratory Endpoints
WAS:
PGI-S and PGI-C will be analyzed using Cochran Mantel Haenszel test with PGI S using the baseline score.
IS AMENDED TO:
PGI-S and PGI-C will be analyzed using Cochran Mantel Haenszel test with PGI-S using the adjusted for baseline score.

IIB. Nonsubstantial Changes

II. Contact Details of Key Sponsor's Personnel

WAS:

CRO Medical Monitor/Study Physician:	
PPD
 
ICON Clinical Research
 
PPD
 
PPD
 
ICON Clinical Research
 
PPD
 
PPD
 
Astellas Pharma Global Development, Inc. [name] [name] USA
 
PPD

--------------------------------------	---

IS AMENDED TO:

5.1.4 Treatment Compliance

WAS:

Subjects who are less than 80% compliant with the dosage regimen for any 2 consecutive visit periods during the study should be considered withdrawn from the study.

IS AMENDED TO:

Subjects who are less than 80% compliant with the dosage regimen for any 2 consecutive visit periods during the study should be considered **for withdrawal**~~withdawn~~ from the study.

| VMS | Vasomotor Symptoms |
| WPAI | Work Productivity and Activity Impairment |

List of Key Terms

| Terms | Definition of terms | |
|----------------------------------|---|--|
| Double-blind Treatment Period | The 12 weeks of treatment after the first administration of study drug and prior to first administration of study drug in the extension period. Only this period contains a placebo treatment. | |
| Extension Treatment Period | Period of time after the first administration of study drug in the extension period after completing 12 weeks of placebo-controlled double-blind treatment until the last dose of the study drug (at Week-52 or early discontinuation). | |
| Follow-up Period | Period of time after the last dose of study drug or last assessment of the protocol. Additional safety data and follow-up observations for sustained adverse events are conducted during this period. | |

1 INTRODUCTION

This Statistical Analysis Plan (SAP) contains technical and detailed elaboration of the principal features of the analysis described in the protocol, and includes procedures for executing the statistical analysis to fulfil the objectives of the study.

This SAP describes the plans for data summary of the 52-week study including the 40-week extension treatment period after completing 12-week double-blind placebo-controlled treatment period. These analyses may be conducted prior to all subjects completing the full 52-week study, if needed. A separate SAP describes the analysis of the 12-week double-blind study data period.

The SAP v1.0 was approved prior to the database lock for the 12-week analysis. This updated SAP will be approved prior to the final study database lock. The SAP will be finalized before unblinding the subject treatment assignments.

Changes from the planned analyses in the finalized SAP that impact the statistical analyses will be documented and justified in the Clinical Study Report (CSR).

2 STUDY OBJECTIVE(S) AND DESIGN

2.1 Study Objective(s)

Note that the analyses for many of these objectives have been described in the SAP for the double-blind placebo-controlled study period for 12-week analysis. All protocol objectives are listed below but the specific endpoints in this SAP have been restricted to those extending beyond the double-blind treatment period. The objectives of the study beyond the double-blind treatment period are to describe efficacy and safety for subjects exposed to fezolinetant for up to 52 weeks.

Primary objective:

- To evaluate the efficacy of fezolinetant versus placebo on the frequency and severity of moderate to severe vasomotor symptoms (VMS).
 - The estimand of the primary objective will use a hypothetical strategy and compare patients as though they had continued on the assigned treatment.

Key secondary objective:

• To evaluate the efficacy of fezolinetant versus placebo on patient-reported sleep disturbance.

Secondary objectives:

- To evaluate the effect of fezolinetant versus placebo on the frequency and severity of moderate to severe VMS at weekly time points.
- To evaluate the safety and tolerability of fezolinetant.

Exploratory objectives:

- To evaluate population pharmacokinetics (popPK) of fezolinetant and metabolite ES259564.
- To evaluate the effect of fezolinetant on pharmacodynamic markers.
- To evaluate the efficacy of fezolinetant versus placebo on the frequency and severity of mild, moderate and severe VMS.
- To evaluate the short-term and sustained effects of fezolinetant versus placebo on patient-reported sleep disturbance.
- To evaluate the effect of fezolinetant versus placebo on the following patient-reported outcomes (PROs): global assessments of VMS and sleep disturbance, overall sleep-wake function, quality of life and work productivity.

2.2 Study Design

This is a randomized, 12-week double-blind, placebo-controlled, parallel group, multicenter clinical study to assess the efficacy and safety of fezolinetant in women suffering from moderate to severe VMS associated with menopause. Approximately 450 subjects will be enrolled into this study, 150 subjects per treatment arm. Duration of treatment is 52 weeks. After completing 12 weeks of treatment, subjects on placebo will be reassigned to 30 mg or 45 mg of active treatment in an extension treatment period through end of study. Subjects who were already randomized on an active arm will continue on their assigned dose for the remaining 40 weeks of treatment. Following the completion (or early discontinuation [ED]) of the treatment period (week 52), subjects will complete an end of treatment (EOT; or ED) visit and final safety follow-up visit 3 weeks after the last dose of study drug is administered (week 55).

Details of the schedule of clinical assessments are available in the protocol.

2.3 Randomization

The first 12 weeks of the study are double blind. Subjects will be randomized to receive fezolinetant or placebo in a blinded fashion such that neither the investigator, sponsor's study management team, clinical staff, nor the subject will know which agent is being administered. The randomization number will be assigned based on information obtained from the Interactive Response Technology (IRT).

Subjects will be randomized in a 1:1:1 ratio to a treatment arm according to the randomization schedules and stratified by smoking status (current smoker vs former/never) through IRT. Subjects who complete the 12-week treatment period and have received placebo will be re-randomized to either fezolinetant 30 mg or 45 mg for the extension period. The assigned treatment in the extension period will remain blinded to the site personnel and participating subjects. The site personnel will dispense the treatment according to the IRT system's assignment. Specific procedures for randomization through the IRT are contained in the IRT specifications manual.

3 SAMPLE SIZE

A total of 450 subjects are planned to be randomized; 150 subjects in each of the three treatment arms. The subjects for the analyses covered in this SAP are determined by the number of subjects who receive at least one dose of fezolinetant during the study. Subjects originally randomized to placebo will only be included if they complete the double-blind treatment phase, are re-randomized, and receive at least one dose of fezolinetant during the study the study, unless otherwise specified.

The sample size of 450 subjects was driven by the double-blind comparisons to placebo at week 4 and week 12. See the 12-week analysis SAP for sample size details.

4 ANALYSIS SETS

In accordance with International Conference on Harmonization (ICH) recommendations in guidelines E3 and E9, the following analysis sets will be used for the analyses.

4.1 Full Analysis Set

The full analysis set for the 52-week analysis will consist of all subjects who are randomized and receive at least 1 dose of fezolinetant during either the double-blind or the extension period (FAS_F). This will be the primary analysis set for descriptive efficacy analyses. The randomized treatment for each subject will be used for summaries by treatment group based on the FAS_F, even if a subject erroneously received a different treatment.

4.2 Safety Analysis Set

The safety analysis set for the 52-week analysis will consist of all subjects who are randomized and receive at least 1 dose of fezolinetant during either the double-blind or the extension period (SAF_F), and will be used for safety analyses. A subject erroneously receiving a treatment different from their randomized treatment will be assigned to the treatment group that the subject received as first dose.

The SAF_F will be used for summaries of demographic and baseline characteristics and all safety and tolerability related variables.

4.3 **Per Protocol Set**

Per protocol analysis sets are not applicable beyond the double-blind treatment period.

4.4 Pharmacokinetics Analysis Set

The PKAS will be defined in a separate analysis plan. Results of the population PK analysis will not be reported in the Clinical Study Report but in a separate population PK report.

4.5 Pharmacodynamic Analysis Set

The pharmacodynamic analysis set for the extension (PDAS_F) will include the subjects from the administered population (received at least 1 dose of fezolinetant during either the double-blind or the extension period) for whom sufficient pharmacodynamic measurements

were collected during the study. The PDAS_F will be used for all analyses of pharmacodynamic data (e.g., sex hormones).

5 ENDPOINTS

The calculation of efficacy baseline for VMS frequency and severity is described in the 12-week analysis SAP, and will be calculated based on the number of moderate to severe hot flashes in the 10 days immediately prior to randomization.

For general efficacy endpoints collected at visits, the last non-missing assessment on or prior to the first dose of study treatment (investigational product or placebo) is the baseline.

For all general safety endpoints, in contrast, the baseline value will be the last non-missing value taken on or prior to first dose of fezolinetant.

Note that the baseline calculations differ between efficacy and safety analyses. The efficacy endpoints are subjective and there is expected to be a non-ignorable placebo effect, so the entire double-blind portion of the study is considered post-baseline for all subjects. For safety endpoints, any changes while on placebo during the double-blind portion of the study are expected to be within-subject variation and changes from baseline will be assessed beginning with exposure to fezolinetant.

The table below provides additional details regarding the baselines for specific endpoints. The terms R_{BL} and $WK12_{BL}$ indicate where the baseline is established, where R_{BL} is initial randomization and $WK12_{BL}$ is the start of the extension period at Week 12.

| Endpoint | Baseline | | |
|--|-----------------|-----------------|--|
| - | fezolinetant / | placebo / | |
| | fezolinetant | fezolinetant | |
| General efficacy | R _{BL} | R _{BL} | |
| General safety and TVU | R _{BL} | $WK12_{BL}$ | |
| Hormones | R _{BL} | $WK12_{BL}$ | |
| Demographics | R _{BL} | R_{BL} | |
| Medical history | R _{BL} | R _{BL} | |
| Prior medications | R _{BL} | $WK12_{BL}$ | |
| Concomitant medications | R _{BL} | $WK12_{BL}$ | |
| Study drug exposure and compliance | R _{BL} | $WK12_{BL}$ | |
| TEAE | R _{BL} | $WK12_{BL}$ | |
| Clinical lab summary shifts and liver safety assessments | R _{BL} | $WK12_{BL}$ | |
| Protocol deviations | R _{BL} | R _{BL} | |
| Biopsy (Listing only) | R _{BL} | R _{BL} | |

The 12-week double-blind placebo period will be completely described as part of the treatment comparisons within the 12-week double-blind analyses. As a result, all endpoints in the 52-week analysis are from the first dose of fezolinetant and onward (see Section 6.10 for additional details).

The ePRO daily diary, ePRO visit-based questionnaires, and CRF-based endpoints are all described in the 12-week analysis SAP.

Only analyses pertaining to endpoints that extend to time points beyond the 12-week doubleblind period will be described in this SAP for the 52-week study.

The analysis visits for each endpoint and their corresponding definitions of calculation windows are in Section 6.10.1.1 (Efficacy Analysis Windows).

5.1 Primary Efficacy Endpoints

There is no primary efficacy endpoint beyond the double-blind treatment period. However, some VMS definitions from the 12-week analysis SAP are repeated below as the subjects continue to record their VMS symptoms in their electronic diary during the extension treatment period.

Subjects will record the number of vasomotor symptoms and severity of each vasomotor symptom via the ePRO daily diary.

The severity of an individual VMS is defined as follows [FDA Draft Guidance for Industry, 2003 and EMA CHMP Guideline, 2005]:

- Mild: sensation of heat without sweating
- Moderate: sensation of heat with sweating, able to continue activity
- Severe: sensation of heat with sweating, causing cessation of activity

For both post-baseline frequency and severity, a daily average per week will be derived if any information for 4 or more days was reported.

5.2 Secondary Efficacy Endpoints

5.2.1 Key Secondary Endpoint

There is no key secondary efficacy endpoint beyond the double-blind treatment period.

5.2.2 Secondary Endpoints

The secondary efficacy objectives that extend beyond the double-blind treatment period and examine the effect of fezolinetant over time are the following:

- Mean change in the frequency of moderate to severe VMS from baseline to week 24 (descriptive)
- Mean change in the Severity of moderate to severe VMS from baseline to week 24 (descriptive)

These will be described as a time point of particular interest within the exploratory VMS endpoint below.

5.3 Exploratory Efficacy Endpoints

The exploratory efficacy objectives that extend beyond the double-blind treatment period and examine the effect of fezolinetant over time are the following:

- Mean change in the frequency and severity of moderate and severe VMS from baseline to each analysis visit in the extension period and the follow-up visit
 - Earlier time points will also be presented for completeness

- Change in serum concentrations of sex hormones and sex hormone-binding globulin (SHBG) from baseline to each analysis visit
- Mean change in serum concentrations of bone specific alkaline phosphatase (BSAP), procollagen type 1 amino-terminal propeptide (P1NP) and carboxy-terminal telopeptide of type I collagen (CTX) from baseline to each analysis visit
- Plasma concentrations of fezolinetant and metabolite ES259564 at pre-specified time points
- Score on the Patient Global Impression of Change (PGI-C) in VMS at each visit
- Mean change on the PROMIS SD SF 8b total score from baseline to each visit
- Mean change on the Patient-Reported Outcomes Measurement Information System Sleep-Related Impairment Short Form 8a (PROMIS SRI SF 8a) total score from baseline to each visit
- Score on the Patient Global Impression of Severity in Sleep Disturbance (PGI-S SD) at each visit
- Score on the Patient Global Impression of Change in Sleep Disturbance (PGI-C SD) to each visit
- Mean change on the Menopause-Specific Quality of Life (MENQOL) total score from baseline to each visit
- Mean change on the MENQOL domain scores from baseline to each visit
- Mean change on the Euro-Qol 5D-5L (EQ-5D-5L) Visual Analog Scale (VAS) from baseline to each visit
- Mean change on the Work Productivity and Activity Impairment questionnaire specific to VMS (WPAI-VMS) domain scores from baseline to each visit.

5.4 Safety Endpoints

Safety evaluations will include the following endpoints, but are not limited to:

- Frequency and severity of AEs
- TVUs and endometrial biopsy findings
- Change from baseline to each timepoint in vital signs: sitting systolic and diastolic blood pressure and pulse rate
- Change from baseline to each timepoint in ECG parameters
- Change from baseline to each timepoint in laboratory tests: hematology, biochemistry and urinalysis

6 STATISTICAL METHODOLOGY

6.1 General Considerations

As a result of this study design and the re-randomization of subjects originally assigned to placebo, there are four treatment groups which will be described in the 52-week analysis:

• Subjects originally randomized to 30 mg: 30 mg => 30 mg; per protocol, these subjects will have up to 12 months of fezolinetant exposure.

- Subjects randomized to placebo who will be re-randomized to 30 mg: placebo => 30 mg; per protocol, these subjects will have up to 9 months of fezolinetant exposure.
- Subjects originally randomized to 45 mg: 45 mg => 45 mg; per protocol, these subjects will have up to 12 months of fezolinetant exposure.
- Subjects randomized to placebo who will be re-randomized to 45 mg: placebo => 45 mg; per protocol, these subjects will have up to 9 months of fezolinetant exposure.

Continuous data will be summarized descriptively including the number of subjects (n), mean, standard deviation (SD), median, minimum and maximum. Categorical data will be summarized by frequencies and percentages. Percentages by categories will be based on the number of subjects with no missing data, i.e., the percentages for the non-missing categories will add up to 100%.

All summaries are descriptive and there are no statistical comparisons within the 52-week analyses.

All data summarization and analyses will be performed using SAS® on Unix. Specifications for table, figures, and data listing formats can be found in the Tables Listings and Figures (TLF) specifications.

As mentioned in the introduction, this analysis plan describes the analyses of the entire 52-week study for subjects who received fezolinetant, excluding the 12-week double blind analyses which is planned in a separate SAP.

Listings will include baseline data and data from first dose of fezolinetant, unless otherwise noted.

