6.5 Analysis of Safety

All analysis of safety will be presented by the four treatment groups, as described in Section 6.1 (General Considerations), for SAF_F, unless specified otherwise. For analyses by visit, the visit windows from Section 6.10.1.2 will be applied, and they are all defined relative to the start of fezolinetant. Except for adverse events and follow-up visit data, only data up to one day after the last dose date will be considered for the analyses.

The baseline value for safety endpoint will be the last non-missing value taken on or prior to first dose of fezolinetant unless otherwise noted.

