6.5.1 Adverse Events

TEAE is defined as an AE observed after starting administration of fezolinetant and up to 21 days after the last dose of study drug.

A study drug-related TEAE is defined as any TEAE with a causal relationship of YES by the investigator.

The sponsor has a list of events that they classify as "always serious" events. If an AE is reported that is considered by the sponsor to be an SAE per this classification as "always serious", the AE will be treated as an SAE in tables and listings, and flagged as 'always serious' in AE listings.

An overview table will include the following

- Number of TEAEs,
- Number and percentage of subjects with TEAEs,
- Number of drug related TEAEs,
- Number and percentage of subjects with drug related TEAEs,
- Number of serious TEAEs,
- Number and percentage of subjects with serious TEAEs,
- Number of serious drug related TEAEs,
- Number and percentage of subjects with serious drug related TEAEs,
- Number of TEAEs leading to permanent discontinuation of study drug,
- Number and percentage of subjects with TEAEs leading to permanent discontinuation of study drug, and
- Number of deaths.

The number and percentage of subjects with TEAEs in the following AE categories will be summarized for each treatment group by system organ class (SOC), high level term (HLT) and preferred term (PT):

- TEAEs
- drug related TEAEs.

The number and percentage of subjects with TEAEs in the following AE categories will be summarized by SOC and PT:

- serious TEAEs,
- drug related serious TEAEs,
- TEAEs leading to permanent discontinuation of study drug,
- drug related TEAEs leading to permanent discontinuation of study drug,
- TEAEs that equal to or exceed a threshold of 5.0% in any treatment group (threshold is based on PT).
- TEAEs excluding serious adverse events that equal to or exceed a threshold of 5.0% in any treatment group.

The number and percentage of subjects with TEAEs, as classified by PT only, will be summarized for each treatment group.

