6.5.2.1 Liver Safety Assessment

The liver safety assessments will be summarized by the categories below based on the measurements from Alkaline Phosphatase (ALP), Alanine Transaminase (ALT), total bilirubin, Aspartate Transaminase (AST) and their combination. These parameters will be based on measurements from a central laboratory.

The subject's highest value during the entire active-dose study period (from day of first dose of fezolinetant until last dose of extension treatment period + 1 day) will be used.

- ALT > 3xULN, > 5xULN, > 8xULN, > 10xULN, > 20xULN
- AST > 3xULN, > 5xULN, > 8xULN, > 10xULN, > 20xULN
- ALT or AST > 3xULN, > 5xULN, > 8xULN, > 10xULN, > 20xULN
- ALP > 1.5 xULN
- Total Bilirubin > 2xULN
- (ALT or AST > 3xULN) and Total Bilirubin > 2xULN
- (ALT or AST > 3xULN) and ALP < 2xULN and Total Bilirubin > 2xULN

The last 2 criteria where 2 or more parameters are evaluated will be with the measurements on the same day or up to 1 day apart. The denominator for each criterion will be the number of subjects who have at least one value during the active-dose study period. The number and percentage of subjects meeting the criteria during the active-dose study period will be summarized by treatment group.

Due to the COVID-19 pandemic, subjects might not have been able to visit the clinical site and have clinical laboratory tests taken at the clinical site and evaluated by the central laboratory, in this case clinical laboratory tests were performed taken by a local laboratory. The liver biochemistry safety assessments will be summarized including central and locally collected laboratory data due to the COVID-19 pandemic. This analysis is considered the primary analysis for the liver safety assessment.

As a secondary analysis for liver biochemistry, the analysis will be repeated with the data evaluated by the central laboratory but excluding the data that are impacted by COVID-19 pandemic, which include the data recorded after the subjects were diagnosed of COVID-19, after study drug discontinuation due to COVID-19, during dose interruption due to COVID-19, and visits that are out of protocol windows or data collected via home visits due to COVID-19 recorded in the eCRF.

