6.10.1.1 Efficacy Analysis Windows

For the analysis windows, the last day is always the last day of exposure to overall study treatment. For VMS diary data the last day of exposure includes events reported until

8:00AM the following day. For example, the Week 1 average will include diary data from 8AM on Day 1 through 7:59AM on Day 8.

For both VMS and non-VMS efficacy, the end of overall treatment is defined as the last day of treatment (e.g., discontinued study or entered follow-up period) and the follow-up period begins at last overall treatment + 1 day.

| Analysis study week | Analysis window |
|---------------------|--|
| Baseline | Non-missing days from D-10 up to and including D-1 |
| Week 1 | FD1 to FD7 |
| Week 2 | FD8 to FD14 |
| Week 3 | FD15 to FD21 |
| Week 4 | FD22 to FD28 |
| Week 5 | FD29 to FD35 |
| Week 6 | FD36 to FD42 |
| Week 7 | FD43 to FD49 |
| Week 8 | FD50 to FD56 |
| Week 9 | FD57 to FD63 |
| Week 10 | FD64 to FD70 |
| Week 11 | FD71 to FD77 |
| Week 12 | FD78 to FD84 |
| Week 16 | FD110 to FD116 |
| Week 20 | FD138 to FD144 |
| Week 24 | FD166 to FD172 |
| Week 28 | FD194 to FD200 |
| Week 32 | FD222 to FD228 |
| Week 36 | FD250 to FD256 |
| Week 40 | FD278 to FD284 |
| Week 44 | FD306 to FD312 |
| Week 48 | FD334 to FD340 |
| Week 52 | FD362 to FD368 |
| Week 53 (Follow-up) | FUD1 to FUD7 |
| Week 54 (Follow-up) | FUD8 to FUD14 |
| Week 55 (Follow-up) | FUD15 to FUD21 |

The study week determination for the vasomotor symptoms data is based on the following:

Calculations for weeks up through Week 12 end on the last day of the study week. Calculations for weeks beyond the double-blind treatment period are centered about protocol-specified visits to match visit-based efficacy assessments. For example, the Week 12 analysis window ends on FD84 (7*12=84), but the Week 16 visit is centered around protocol specified FD113 (FD110 to FD116). Calculations in the follow-up period end on the last day of the study week, based on study days in the follow-up period.

Weeks 44, 48 and 52 will be missing for subjects randomized to placebo during the doubleblind treatment period because they are only on active treatment for 40 weeks.

A weekly average will be calculated if any information, including zero VMS events, was reported for 4 or more days.

All other efficacy assessments, including those from unscheduled visits and regardless of visit label, will be allocated to analysis visits based on the table below:

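### The 52-week cumulative safety tables give unadjusted percentages for groups with up to 52 and up to 40 weeks of fezolinetant, so columns of different duration are not comparable as they stand

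*SAP*

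**What the plan says.** Section 6.1 of the 52-week SAP defines four groups by exposure history. For the two groups that started on 30 mg or 45 mg it says "per protocol, these subjects will have up to 12 months of fezolinetant exposure"; for the two groups re-randomized from placebo it says "per protocol, these subjects will have up to 9 months of fezolinetant exposure". Section 2.2 gives the total ("Duration of treatment is 52 weeks"). Section 6.10.1.1 states the shorter period in weeks, explaining that late visits will be missing for ex-placebo women "because they are only on active treatment for 40 weeks".

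Section 6.5 sets the layout: "All analysis of safety will be presented by the four treatment groups". Section 6.5.1 counts as treatment-emergent "an AE observed after starting administration of fezolinetant and up to 21 days after the last dose of study drug". Its tables give number and percentage of women, for example "The number and percentage of subjects with TEAEs, as classified by PT only, will be summarized for each treatment group". The same statistic is used for serious events, events leading to discontinuation and events of special interest. Event counts are added in the overview and in the tables by severity and relationship.

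Section 6.5.2.1 takes each woman's highest liver value from first fezolinetant dose to last dose + 1 day, and sets the denominator: "The denominator for each criterion will be the number of subjects who have at least one value during the active-dose study period".

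Section 6.3 tabulates exposure duration by group. Neither the protocol nor either SAP specifies a patient-year denominator, a time-to-first-event estimate, or adverse event or liver tables cut at a common length of exposure.

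**The concern.** A cumulative percentage grows with the time over which events can be recorded. Two columns have 12 more planned weeks on drug than the other two, so the same underlying risk produces a larger percentage in them. For the liver table the number of samples differs as well as the time. Section 2.1 of the 52-week SAP says the aim beyond week 12 is to describe efficacy and safety for women exposed for up to 52 weeks, and section 1.5 of the protocol names liver injury as an important potential risk. Readers will look along the rows of these tables even though no test is planned. A 52-week column could then look worse than a 40-week column, or a combined figure made later from both could blur the two durations, with nothing in the table to show how much is due to time on drug.

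**Working it through.** **1. The plan's own figures.** 52 − 12 = 40 weeks for the ex-placebo groups. With 30.44 days per month, 40 × 7 / 30.44 = 9.2 months and 52 × 7 / 30.44 = 12.0 months. Both stated durations reproduce.

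**2. Exposure ratio.** On treatment: 52 / 40 = 1.30. With the 21-day (3-week) adverse event tail: 55 / 43 = 1.28.

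**3. Effect on a crude percentage.** The documents give no event risks for this period, so the risks below are assumptions, shown over a range. Assume the same constant hazard in both groups and full follow-up. If p is the risk over the longer period, the risk over the shorter one is 1 − (1 − p)^(40/52), or 1 − (1 − p)^(43/55) with the tail. For example, 1 − 0.80^(40/52) = 15.8%.

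| Assumed risk, longer group | Shorter group, 52 vs 40 weeks | Ratio | Shorter group, 55 vs 43 weeks | Ratio |
|---|---|---|---|---|
| 1.0% | 0.77% | 1.30 | 0.78% | 1.28 |
| 5.0% | 3.9% | 1.29 | 3.9% | 1.27 |
| 20% | 15.8% | 1.27 | 16.0% | 1.25 |
| 40% | 32.5% | 1.23 | 32.9% | 1.21 |

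The absolute gap on the 52 vs 40 week scale runs from 0.2 points (1.0 − 0.77) to 7.5 points (40 − 32.5).

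**4. What a rate would show.** Under the same assumption a 20% risk over 52 weeks is a hazard of −ln(0.80)/52 = 0.00429 per week. With 52.18 weeks per year that is 22.4 per 100 patient-years in both groups.

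**5. Drop-out.** The only planning value is 20% before week 12 (12-week SAP, section 3); none is given for the extension. With a constant drop-out rate g, mean exposure over T weeks is (1 − exp(−gT))/g. Four scenarios:

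- 20% lost over 52 weeks: 46.6 vs 36.8 weeks, ratio 1.27.
- 20% per 12 weeks continued throughout: 33.3 vs 28.2 weeks, ratio 1.18.
- 20% lost in the first 12 weeks on fezolinetant in both groups, none later: 42.8 vs 33.2 weeks, ratio 1.29.
- 20% lost early in the original active arms only: 42.8 vs 40 weeks, ratio 1.07.

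**6. Liver samples.** From the protocol's Schedule of Assessments, women first randomized to fezolinetant have scheduled post-baseline liver tests on drug at weeks 2, 4, 8, 12 and 14 and ten more from week 16 to week 52: 5 + 10 = 15. Ex-placebo women have week 14 and the same ten: 11.

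**7. Early events.** Suppose (an assumption) 5% of women in each group have a first event at week 6 and nobody drops out. Crude percentages are correctly equal. Mean time at risk is 0.95 × 52 + 0.05 × 6 = 49.7 weeks against 0.95 × 40 + 0.05 × 6 = 38.3 weeks. The rates are 0.05 / 49.7 × 52.18 × 100 = 5.2 and 0.05 / 38.3 × 52.18 × 100 = 6.8 per 100 patient-years, a false 1.3-fold excess in the 40-week group. A patient-year rate alone is therefore not a safe remedy for events that cluster early.

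**The case against.** The plan keeps the groups apart by exposure history, states each group's planned exposure, tabulates actual duration, and declares every 52-week summary descriptive. Section 7.5.1 of the protocol itself asks for number and percentage. All of this stands, and it makes this a matter of presentation and interpretation, not of error rates.

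Four stronger readings are tempting, and the documents do not support them:

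- A reader might infer that the comparison of doses is distorted. It is not, within a duration: 30 mg throughout against 45 mg throughout is 52 vs 52 planned weeks, and the two ex-placebo groups are 40 vs 40.
- A reader might infer that the plan pools women by dose across durations. No pooled-dose safety column is specified.
- A reader might infer that crude percentages are the only safety output. Event counts are given too, and laboratory, vital sign, ECG and C-SSRS summaries by visit use windows counted from first fezolinetant dose, so they can be read at equal exposure.
- A reader might infer that any gap between a 52-week and a 40-week column is due to exposure alone. That needs a constant common hazard and similar drop-out. Section 3 also admits ex-placebo women only if they completed the 12-week period, a selection difference that no exposure adjustment removes.

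Timing matters as well. Section 1.5 of the protocol places seven of the phase 2b transaminase rises at 4 to 8 weeks, where the crude percentage is hardly affected by later exposure. Finally, the table specifications are a separate document not available here and might contain further displays; the SAP does not call for them.

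**Conclusion.** The point holds for the cumulative event tables: treatment-emergent events, serious events, events leading to discontinuation, events of special interest and liver threshold crossings. Read across durations, or if the columns are later combined, these percentages mix risk with time on drug. Under a common constant hazard and full follow-up the inflation is at most about 1.3-fold and falls as events become more common. Drop-out could bring the exposure ratio down to 1.07 in the most favourable scenario examined, and events confined to early treatment are hardly affected. The event risks are assumptions. Priority is low to moderate: the difference is disclosed and nothing is tested, but the output describes long-term safety and the correction is cheap.

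**What to change.** **Section 6.5.1.** For treatment-emergent events, serious events, events leading to discontinuation and events of special interest, add by the four groups the number of women with a first event per 100 patient-years at risk. Time at risk runs from first fezolinetant dose to first event or last dose + 21 days, whichever comes first.

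**Sections 6.5.1 and 6.5.2.1.** Add the same adverse event and liver tables limited to the first 40 weeks of fezolinetant in every group, or time-to-first-event estimates. Any liver person-time should end at last dose + 1 day, to match the liver window; the 21-day tail would add time in which no liver crossing can be counted. Word the liver cut-off so that the scheduled 40-week sample counts in all groups. With a first extension dose on day 85, the ex-placebo women's day-365 sample falls on fezolinetant day 365 − 85 + 1 = 281, one day after 40 × 7 = 280. The SAP's own Week 40 safety window (days 268 to 295) would cover it. Scheduled liver samples are then 12 (weeks 2, 4, 8, 12 and 14, and seven from week 16 to week 40) against 11, instead of 15 against 11.

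**Keep the crude percentages.**

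**Cost.** A few more table columns, built from dosing, event and sample dates that the plan already needs. Rates assume a roughly constant hazard and can mislead for early-onset events such as transaminase rises, which is why the 40-week tables are needed beside them. Neither display removes the selection of ex-placebo women who completed week 12; a footnote should say so.
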